Diagnosis and monitoring of eosinophilic esophagitis using the Cytosponge

NCT02114606

Protocol Version Date:

25 September 2020

DIAGNOSIS AND MONITORING OF EOSINOPHILIC ESOPHAGITIS USING THE CYTOSPONGE

Principal Investigator

[name], MPH
Assistant Professor of Medicine and Epidemiology
University of North Carolina School of Medicine
[name]
[name]
[contact]

Co-Investigators

[name]
Mayo Clinic Rochester
Rochester, MN

[name], MA, MD
Cambridge University
Cambridge, U.K.

[name], MPH
University of North Carolina School of Medicine
Chapel Hill, NC

Funding Sponsor:

CURED (Campaign Urging Research for Eosinophilic Disease) Foundation

UNC IRB Number:

13-3521

Protocol Version:

4.0

Protocol Version Date:

25 September 2020

SIGNATURE PAGE

The signature below constitutes the approval of this protocol and the attachments, and provides the necessary assurances that this trial will be conducted according to all stipulations of the protocol, including all statements regarding confidentiality, and according to local legal and regulatory requirements and applicable US federal regulations and ICH guidelines.

Principal Investigator or Clinical Site Investigator:

Signed:

Date:

Name:

Title:

Summary of Changes

Version 4.0 dated 25Sep2020	
Study Summary	Objectives and methodology updated according to changes made to these sections of the protocol.
2.0 Study Objectives	Aim 2 removed as the scope of the study was limited by device availability and aim 2 was unable to be evaluated with available data.
3.1 General Design	Reference to Aim 2 removed.
3.4 Secondary Outcomes	Added “agreement between cytosponge and endoscopic biopsy as measured by kappa.” Revised secondary outcome to clarify measures used to assess acceptability.
6.1 Sample Size Determination	Removed reference to Aim 2.
6.2 Statistical Methods	Removed reference to Aim 2.
Administrative Changes	Administrative changes to protocol version and version dates throughout.
Version 3.0 dated 05Sep2017	
3.1 General Design	Additional analyses on samples has been added.
Administrative Changes	Administrative changes to protocol version and version dates throughout as well as updating table of contents and section numbers.
Version 2.0 dated 05Oct2016	
Study Summary 6.1 Sample Size Determination	Increased enrollment from 100 to up to 150 to account for any potential issues with sample quality and additional safety assessments.

IRB	Institutional Review Board
VAS	Visual Analog Scale

Study Summary

Title	Diagnosis and monitoring of eosinophilic esophagitis using the Cytosponge
Methodology	This will be a prospective cohort study, with patient enrollment conducted at UNC and Mayo Clinic by Drs. [name] and [name], and further sample analysis performed by [name]. In Aim 1, patients with eosinophilic esophagitis (EoE) or suspected EoE will be enrolled, tissue will be obtained from both the Cytosponge and routine care endoscopy, and the methods will be compared for a single time point to determine accuracy of Cytosponge for quantifying esophageal eosinophil counts. The patients who are being treated will be followed and tissue will be assessed over time with both Cytosponge and routine care endoscopy to determine the utility of Cytosponge for monitoring treatment response in patients with EoE. For all patients, safety will be monitored and subjects will complete a survey about the acceptability of Cytosponge (Aim 2).
Study Duration	2 Years
Study Center(s)	University of North Carolina, Chapel Hill, NC Mayo Clinic, Rochester MN
Objectives	
Aim 1: To determine the accuracy of Cytosponge for quantifying esophageal eosinophil counts in patients with active EoE, as compared to endoscopy with biopsy as the gold standard.
 
Aim 2: To determine the safety and acceptability of Cytosponge for patients with EoE.

Number of Subjects	150
Diagnosis and Main Inclusion Criteria	
Inclusion Criteria:
 
1. Able to read, comprehend, and complete the informed consent form2. Male or female subjects, age 18-80 years,3. Suspected EoE or has a diagnosis of EoE with current active disease, 
Exclusion Criteria:
 
1. History of esophageal stricture precluding passage of the endoscope or sponge,2. Pregnancy, or planned pregnancy during the course of the study,3. Any history of esophageal varices, liver impairment of moderate or worse severity (Child's- Pugh class B & C) or evidence of varices noted on any past endoscopy,4. Any history of esophageal surgery, except for uncomplicated fundoplication5. History of coagulopathy, with INR>1.3 and/or platelet count of <75,000.6. Current use of blood thinners such as coumadin, warfarin, clopidogrel, heparin and/or low molecular weight heparin (requires discontinuation of medication 7 days prior to and 7 days after esophagogastroduodenoscopy [EGD] and Cytosponge administration, aspirin use is OK).7. Are allergic to local anesthetics such as lidocaine (these subjects may opt not to receive the optional lidocaine gargle prior to the Cytosponge administration and still be eligible).8. Have not fasted the night before administration of the Cytosponge.9. History of perforation.

Statistical Methodology	
Aim 1: To test the hypothesis that the Cytosponge accurately quantifies esophageal eosinophil counts in patients with active EoE, the maximum eosinophil counts from the Cytosponge and endoscopic biopsy will be compared by calculating the Pearson coefficient of correlation. In addition, patients will be categorized as having an eosinophil count either above or below 15 eos/hpf (the current diagnostic threshold). Agreement between patients above and below this threshold for Cytosponge and endoscopic biopsy will be measured using the kappa statistic. If eosinophil counts are not normally distributed, non-parametric methods will be used.
 
Aim 2: Summary statistics will be calculated to describe adverse events and the tolerability of the Cytosponge. The proportion of subjects who prefer the Cytosponge will be calculated.

-------------------------	--

1 Introduction

This document is a protocol for a human research study. The study will be conducted in accordance with the International Conference on Harmonisation guidelines for Good Clinical Practice (ICH E6), the Code of Federal Regulations on the Protection of Human Subjects (45 CFR Part 46), and applicable federal regulations and institutional policies. All personnel involved in the conduct of this study have completed human subjects protection training.

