The current endoscopic methods for diagnosing and monitoring treatment response in EoE are costly, inconvenient, and risky. Novel diagnostic methods are needed, and the minimally-invasive

Cytosponge holds great promise. It has been shown to be safe and accurate in Barrett's esophagus, it has the advantage (over the string test) of obtaining a true tissue sample, and our preliminary data supports its further study in EoE. The proposed prospective cohort study, conducted by experts in esophageal diseases and EoE, will assess the accuracy of Cytosponge compared to endoscopy and biopsy in EoE, and determine the safety and acceptability of this technique. Use of the Cytosponge would fundamentally change the paradigm for clinical management of EoE by allowing collection of non-

endoscopic esophageal biopsies, thus minimizing the need for invasive testing. It would also facilitate future genetic, mechanistic, and pathogenesis research in EoE.

The specific goals of this study are to assess the safety, acceptability, and accuracy of Cytosponge for diagnosis and monitoring of EoE in comparison to endoscopy and biopsy as the gold standard. To achieve these goals, we will recruit subjects with EoE from both the University of North Carolina ([name]) and from the Mayo Clinic in Rochester where Cytosponge has already been used for EoE ([name]). Our central hypothesis is that the tissue obtained using Cytosponge will show an eosinophilic infiltrate similar to that seen on endoscopic biopsies in patients with active EoE, will have utility to monitor tissue eosinophilia in patients being treated for EoE, and will be safe, acceptable, and preferable for patients when compared with endoscopy. This research will impact clinical practice by fundamentally changing the way EoE is diagnosed and monitored, decreasing the need for costly and invasive endoscopic procedures. Moreover, because this technique readily obtains esophageal tissue, it could greatly facilitate genetic, mechanistic, and pathogenesis research in EoE. providing less invasive and more cost-effective surveillance of this large and growing patient population.

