of Cytosponge in EoE. A total of 20 EoE patients, some with active disease and some with disease in remission to provide a range of disease severity and esophageal eosinophilic infiltration, swallowed the Cytosponge for tissue sampling prior to undergoing standard endoscopy and biopsy. All patients, even those with esophageal strictures, were able to swallow the Cytosponge without problems, and there were no serious adverse events. The first main result was that the tissue samples were adequate for analysis with standard pathology H&E staining (a stain on which eosinophils are bright pink in color; see Figure 3). The second main result was that Cytosponge performed very well compared with endoscopy and biopsy, with a sensitivity of 100% (the Cytosponge picked up all of the cases of EoE that were also found by endoscopy) and a specificity of 70% (there were some cases felt to be EoE on the Cytosponge that were not felt to be EoE on endoscopy). These preliminary data show that the Cytosponge holds great promise for diagnosis and monitoring of treatment in EoE. If tissue can be obtained with this minimally invasive technique, it would fundamentally change the paradigm for clinical management of EoE by minimizing the need for invasive endoscopies.

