3.2 Protocol Map

3.3 Primary Outcomes

The primary outcome variables will be sensitivity and specificity of the cytosponge, as compared against the gold standard of the presence of EoE as detected by upper endoscopy with biopsies.

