5.1.1 Assessments

The following will be completed during the screening/enrollment visit:

- Eligibility review

- Informed consent
- Cytosponge administration
- Visual Analog Scale
- Adverse event assessment
- Routine care upper endoscopy with biopsy
- Enrollment Case Report Form (CRF): This captures demographics including race, ethnicity, gender, and year of birth, relevant EoE medical history including documentation of endoscopic procedures received to date as well as pathology findings and endoscopic history related to current diagnosis.

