6.3 Subject Population for Analysis

The population whose data will be subjected to the study analysis will include all subjects enrolled in this study that completed the Cytosponge administration and have pathology results available from the subsequent routine care endoscopy with biopsy.

7 Safety and Adverse Events

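### The primary sensitivity and specificity pool suspected with already diagnosed active EoE, and no planned analysis separates the two, although accuracy for diagnosis is a stated goal

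*Combined protocol and SAP*

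**What the plan says.** Criterion 3 (Section 4.1, repeated in the Study Summary) reads "Suspected EoE or has a diagnosis of EoE with current active disease". The activity condition applies to diagnosed patients only, and neither section says how activity is established before the study endoscopy.

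Section 3.3 states: "The primary outcome variables will be sensitivity and specificity of the cytosponge", judged against endoscopy with biopsy. Section 6.3 defines one analysis population, "all subjects enrolled in this study that completed the Cytosponge administration" with pathology available from the endoscopy that follows. Section 6.2 specifies correlation and kappa at the 15 eos/hpf threshold, and separate analyses for active and treated patients. It gives no method for sensitivity or specificity and no split by suspected versus diagnosed status.

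The goals at the end of Section 1.2 are to "assess the safety, acceptability, and accuracy of Cytosponge for diagnosis and monitoring of EoE". Section 3.1 recruits consecutive eligible patients, with no quota for either route, and compares the methods at a single time point for Aim 1. Section 5.3 adds later paired samples from treated patients.

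**The concern.** Diagnosis and monitoring concern different patients. The diagnostic question is how the sponge performs in someone being worked up for EoE. A patient who already carries the diagnosis and is judged active has been selected, at least in part, on an earlier reference result. If such patients tend to have higher counts, the sponge will find them more easily, and including them raises sensitivity above what a suspected patient would experience.

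The plan's one existing split does not deal with this. Active versus treated does not isolate suspects, and a suspect whose biopsy is negative fits neither category. A reader of the final report would see one sensitivity, would probably take it as diagnostic accuracy, and could not undo the mixing.

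**Working it through.** **The plan's own figure.** Section 6.1 gives 60 subjects for R = 0.40 with power 0.9 and alpha 0.05. By Fisher's z, two-sided: n = ((1.960 + 1.282)/atanh 0.40)² + 3 = 61.5, and power at 60 is 0.892. That reproduces the stated figure, but it concerns correlation. The documents give no planned size or precision for sensitivity or specificity.

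**Inputs.** N = 60 and the 15 eos/hpf threshold come from Sections 6.1 and 6.2; applying that threshold to sensitivity and specificity is my reading. The rest is assumed and shown as ranges:
- f, share of enrollment already diagnosed: 10% to 75%
- p, share of suspects who are biopsy-positive: 30% to 70%
- a, share of diagnosed subjects biopsy-positive on the study day: 100%, then 90% and 70%

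**Step 1: who supplies the biopsy-positives.** The diagnosed share is w = fa / (fa + (1 − f)p). With a = 100%:

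| f | p = 30% | p = 50% | p = 70% |
|---|---|---|---|
| 10% | 27% | 18% | 14% |
| 25% | 53% | 40% | 32% |
| 50% | 77% | 67% | 59% |
| 75% | 91% | 86% | 81% |

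**Step 2: what pooling does to sensitivity.** Pooled sensitivity = w × Se(diagnosed) + (1 − w) × Se(suspected) = Se(suspected) + w × gap, where gap = Se(diagnosed) − Se(suspected). The shift is w × gap.

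**Step 3: a plausible gap.** I simulated a stable true density (lognormal, median 15 or 40 eos/hpf, log-SD 1.0 or 1.5). The earlier biopsy, the current biopsy and the sponge each had independent log-scale error of SD 0.5 or 0.8, with 4 million draws per setting. I compared P(sponge ≥ 15 given current biopsy ≥ 15) with the same probability when an earlier biopsy was also ≥ 15:
- median 15: 6.0 to 8.6 points higher (for example 0.795 to 0.871)
- median 40: 2.9 to 4.4 points higher (for example 0.915 to 0.944)

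Overall, about 3 to 9 points.

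**Step 4: size of the shift.**
- smallest: 0.137 × 2.9 = 0.4 points
- middle (f = p = 50%): 0.667 × 2.9 to 8.6 = 1.9 to 5.7 points
- largest: 0.909 × 8.6 = 7.8 points

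**Step 5: specificity.** The suspects' share of biopsy-negatives is (1 − f)(1 − p) / [(1 − f)(1 − p) + f(1 − a)]. It is 100% if every diagnosed subject is biopsy-positive. With a = 90% it is 96-98% at f = 10% and 50-70% at f = 75%. With a = 70% it is 90-95% at f = 10%, 50-70% at f = 50% and 25-44% at f = 75%. How near pooled specificity is to the diagnostic value therefore depends on how activity is defined as well as on the case mix.

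**Step 6: price of separating.** Exact (Clopper-Pearson) 95% intervals for illustrative counts: pooled 38/42 = 90% (77-97%); suspects alone 10/12 = 83% (52-98%).

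**The case against.** The strongest reply is that admitting both intended-use groups is not an error, that the pooled table is inferred because Section 6.2 sets out no sensitivity or specificity analysis, and that the whole effect rests on assumed inputs. All of that is fair. It places the gap in Sections 3.3, 6.2 and 6.3 rather than in eligibility. It does not close the gap, because nothing in the plan separates the two routes for the primary outcome.

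Two points weaken the size. Section 1.2 says diagnosis takes two endoscopies, so a suspect may enter with one positive biopsy already, which narrows the contrast simulated. The largest shift, about 8 points, also lies within the width of the illustrative pooled interval at N = 60. But the shift is systematic, and enrolling toward 150 would narrow the interval without removing it.

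Several stronger readings are tempting, and the documents do not support them:
- That sensitivity comes largely from known cases. No case mix is given; at 10% diagnosed they are 14-27% of positives, at 25% they are 32-53%.
- That specificity comes almost only from suspects. This needs activity to mean biopsy-positive on the study day, which is not stated.
- That neither measure informs diagnosis. If negatives are mostly suspects, pooled specificity is close to the diagnostic one.
- That the pilot avoided the problem. Section 1.3 describes 20 EoE patients, "some with active disease and some with disease in remission to provide a range of disease severity and esophageal eosinophilic infiltration", and mentions no suspected patients.
- That monitoring is left without data. Section 5.3 provides follow-up samples at up to 6 time points, and Section 6.2 a separate analysis of treated patients.

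**Conclusion.** The concern holds as a gap in analysis and reporting. The primary sensitivity mixes two populations in unknown proportions, so it cannot be read as sensitivity for diagnosis. The likely direction is upward, by roughly 0.4 to 8 points. That range rests on the assumed case mix (10-75% diagnosed, 30-70% of suspects positive), on all diagnosed subjects being biopsy-positive in the weights, and on a simulation in which severity is stable and sponge and biopsy have equal error. If diagnosed patients in fact sit no further above the threshold than suspects, there is no overstatement, and the objection becomes one of interpretation only.

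Pooled specificity may well be near the diagnostic value, but the plan gives no means of showing it. A reader might go on to infer that criterion 3 should be changed. It need not be: Aim 1 is framed around active EoE, and separate reporting resolves the matter.

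**What to change.** In Sections 3.3 and 6.2 and the Study Summary:
1. Report enrollment-visit sensitivity and specificity separately for suspected subjects (no prior diagnosis) and diagnosed subjects, with counts and exact 95% intervals. Where a group has no biopsy-negatives, say that specificity is not estimable there.
2. Base any claim of diagnostic accuracy on the suspected group, and label the pooled table as describing the enrolled mix.
3. State how current active disease is established at entry.
4. State that follow-up samples stay in the separate treated-patient (monitoring) analysis and do not enter the primary table.

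Leave criterion 3 unchanged. No new data should be needed: the Enrollment CRF in Section 5.1.1 already records EoE history, including "pathology findings and endoscopic history related to current diagnosis". The cost is some wording, one extra table and a less precise diagnostic estimate, since the suspected group alone supplies it.

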1.2 Background

Eosinophilic esophagitis (EoE) is an emerging disease defined by the abnormal presence of eosinophils in the esophageal lining, leading to trouble swallowing (dysphagia), esophageal narrowing (stenosis), and food impaction.¹⁻³ The incidence and prevalence of EoE have risen dramatically,⁴⁻⁷ and EoE is now the most common cause of food impaction in patients presenting to emergency rooms.^{8, 9} In order to diagnose and monitor EoE, upper endoscopy with esophageal tissue biopsy is currently required. Two upper endoscopies are needed to diagnose EoE, the first one to evaluate symptoms and the second one to confirm the diagnosis after treatment with a proton pump inhibitor (anti-acid) medication.³ If a patient is treated with a swallowed ("topical") steroid medication such as budesonide or fluticasone, they undergo a third endoscopy to determine whether the medication was effective.¹⁰⁻¹⁴ If they are treated with an

elimination diet, they will require an endoscopy 6 weeks after the initial elimination, and then another one every 4-6 weeks after each food is added back.¹⁵⁻¹⁷ In some cases this can add up to more than 8-10 endoscopies in a single year. This is costly, inconvenient, and the repeated procedures add risk. New diagnostic methods for EoE are urgently needed.

A novel, minimally invasive a simple, non-endoscopic device, termed the Cytosponge, has been developed for endoscopic screening of subjects at risk for Barrett's Esophagus (a precancerous condition that is a complication of reflux disease),¹⁸ by investigators at the University of Cambridge in the U.K. and is readily applicable to EoE. Cytosponge consists of a foam sponge which is contained within a dissolvable capsule and attached to a string (see Figure 1). The capsule is swallowed, dissolves in the stomach, the sponge expands into a sphere, and after 5 minutes is retrieved by pulling the string. As the sponge is withdrawn, cells along the whole length of the esophagus are collected by the foam sphere; this amounts to obtaining an esophageal biopsy tissue sample, but without doing the endoscopy. The foam sphere, now containing cells, is placed into preservative fluid and processed using standard pathology methods readily available everywhere. Our team has published data about the safety, acceptability, and accuracy of this technique in Barrett's,¹⁸⁻²¹ and we have preliminary data in EoE patients. Of note, Cytosponge differs substantially from the Esophageal String Test (EST), which is also under development for EoE.²² The EST uses a dissolvable capsule and a string to collect fluids secreted from the esophageal lining, but does not capture tissue. Moreover, the EST requires a specialized lab to run advanced tests to measure factors secreted from eosinophils. In contrast, because Cytosponge obtains tissue, it can be used anywhere with existing and inexpensive pathology techniques.

Figure 1: The Cytosponge. The left image shows the expanded sponge. The right image shows the capsule. Both have the string in place.

Figure 2 CytospongeTM (left) and Cytosponge I (right) for comparison

Medtronic, formerly Covidien GI Solutions, has developed a more refined version of the Cytosponge I (referred hereafter as the Cytosponge™ or "Cytosponge"). The Cytosponge was developed from the Cytosponge I specification and design, with the additional priority of a more reproducible manufacturing process, standardization of dimensions, and other quality related features (Figure 2). Because we seek to assess a tool for widespread clinical usage, this study will use the Cytosponge which will be purchased from Covidien GI Solutions (now part of Medtronic).

The current endoscopic methods for diagnosing and monitoring treatment response in EoE are costly, inconvenient, and risky. Novel diagnostic methods are needed, and the minimally-invasive

Cytosponge holds great promise. It has been shown to be safe and accurate in Barrett's esophagus, it has the advantage (over the string test) of obtaining a true tissue sample, and our preliminary data supports its further study in EoE. The proposed prospective cohort study, conducted by experts in esophageal diseases and EoE, will assess the accuracy of Cytosponge compared to endoscopy and biopsy in EoE, and determine the safety and acceptability of this technique. Use of the Cytosponge would fundamentally change the paradigm for clinical management of EoE by allowing collection of non-

endoscopic esophageal biopsies, thus minimizing the need for invasive testing. It would also facilitate future genetic, mechanistic, and pathogenesis research in EoE.

The specific goals of this study are to assess the safety, acceptability, and accuracy of Cytosponge for diagnosis and monitoring of EoE in comparison to endoscopy and biopsy as the gold standard. To achieve these goals, we will recruit subjects with EoE from both the University of North Carolina ([name]) and from the Mayo Clinic in Rochester where Cytosponge has already been used for EoE ([name]). Our central hypothesis is that the tissue obtained using Cytosponge will show an eosinophilic infiltrate similar to that seen on endoscopic biopsies in patients with active EoE, will have utility to monitor tissue eosinophilia in patients being treated for EoE, and will be safe, acceptable, and preferable for patients when compared with endoscopy. This research will impact clinical practice by fundamentally changing the way EoE is diagnosed and monitored, decreasing the need for costly and invasive endoscopic procedures. Moreover, because this technique readily obtains esophageal tissue, it could greatly facilitate genetic, mechanistic, and pathogenesis research in EoE. providing less invasive and more cost-effective surveillance of this large and growing patient population.

